Objectives	
Primary:
 
 Phase 1: To evaluate the safety of the combination of durvalumab with nintedanib in patients with unresectable Stage II/III/oligometastatic IV NSCLC Phase 2: To compare the rate of symptomatic radiation pneumonitis at 6 months after completion of chemoradiation in patients with unresectable Stage II/III/oligometastatic IV NSCLC who completed chemoradiation followed by nintedanib versus placebo. 
Secondary:
 
 To compare the quality of life (QOL) in patients who received nintedanib versus placebo during active treatment until 6 months after completion of treatment. To compare the progression-free survival, overall survival and 1-year progression-free survival rate in patients who received nintedanib versus placebo. To compare pulmonary function test (PFT) results and RP score in patients who received nintedanib versus placebo. To compare the composite index (based on PFT, RP score and QOL) at the end of active treatment and 6 months after completion of treatment between patients who received nintedanib versus placebo. 
Exploratory:
 
 To investigate blood-based biomarkers in evaluating risk of developing radiation pneumonitis as well as the efficacy of nintedanib.
Study Design	
A Phase II, randomized, double-blind, placebo-controlled study of nintedanib as prophylaxis against radiation pneumonitis in patients with advanced NSCLC.
 
Addition of Phase I: With the November 2018 amendment allowing immune checkpoint inhibitor such as durvalumab consolidation therapy, a conventional dose-escalation design will be explored for patients who will be receiving durvalumab. Patients enrolled in the dose-escalation portion must commence nintedanib dosing at the same time as durvalumab is started. Dosing with nintedanib will start at 100 mg BID (see Table 1).

	
For patients who will be receiving durvalumab as standard of care prior to establishment of the recommended phase II dose of this combination, they will NOT undergo randomization (i.e. not blinded to treatment) and will receive active drug (nintedanib) on the first day of the first dose of durvalumab 10mg/kg every 2 weeks for up to 12 months.


Target Accrual and Study Duration
	
Phase I: A maximum of 18 participants will be enrolled to the non-randomized dose escalation portion of this study. The number of participants required is a function of the unknown dose-toxicity relationship.
 
Phase II: A maximum of 99 participants will be enrolled to the randomized Phase 2 portion of this study (excluding patients replaced due to ineligibility or inability to start therapy).
 
Participants will be enrolled from up to 4 sites including Roswell Park.
 
This study is anticipated to complete accrual within 4 years of study activation. Patients will receive either nintedanib or placebo to be administered for 6 months. Patients will be followed for at least one year for initial primary analysis of study outcomes. Patients will be followed for no longer than 2.5 years.


Study Procedures
	
Physical Examination: Baseline, Cycle 1 Day 1, Cycle 2 through Cycle 6 Day 1, anytime when radiation pneumonitis is suspected to have occurred (within the first 6 months after completing radiation therapy), end of active treatment, between 76 to 97 days after last nintedanib/placebo dose, between 166 to 187 days after last nintedanib/placebo dose, long term follow-up.
 
Hematology: Baseline, Cycle 1 Day 1, Cycle 2 through Cycle 6 Day 1, anytime when radiation pneumonitis is suspected to have occurred (within the first 6 months after completing radiation therapy), end of active treatment, between 166 to 187 days after last nintedanib/placebo dose, long term follow-up.
 
Chemistry: Baseline, Cycle 1 Day 1, Cycle 2 through Cycle 6 Day 1, anytime when radiation pneumonitis is suspected to have occurred (within the first 6 months after completing radiation therapy), end of active treatment, between 166 to 187 days after last nintedanib/placebo dose, long term follow-up.
 
Disease Evaluation: Baseline, Cycle 3 Day 1, Cycle 6 Day 1, anytime when radiation pneumonitis is suspected to have occurred (within the first 6 months after completing radiation therapy), between 76 to 97 days after last nintedanib dose, between 166 to 187 days after last nintedanib/placebo dose, and long term follow-up.
 
Performance Status: Baseline, Cycle 1 Day 1, Cycle 2 through Cycle 6 Day 1, anytime when radiation pneumonitis is suspected to have occurred (within the first 6 months after completing radiation therapy), end of active treatment, between 76 to 97 days after last nintedanib/placebo dose, between 166 to 187 days after last nintedanib/placebo dose, long term follow-up.
 
Adverse Events: Baseline, Cycle 1 Day 1, Cycle 2 through Cycle 6 Day 1, anytime when radiation pneumonitis is suspected to have occurred (within the first 6 months after completing radiation therapy), end of active treatment, between 76 to 97 days after last nintedanib/placebo dose, between 166 to

	187 days after last nintedanib/placebo dose, long term follow-up.
Statistical Analysis	
Sample Size Determination: A maximum of 18 participants will be enrolled to the non-randomized dose escalation portion of this study. The number of participants required is a function of the unknown dose-toxicity relationship.
 
A maximum of 99 participants will be enrolled to the randomized Phase 2 portion of this study (excluding patients replaced due to ineligibility or inability to start therapy).
 
Participants will be enrolled from up to 4 sites including Roswell Park. Accrual is expected to take 4 years.
 
Phase II Randomization: Patients will be randomized to either the placebo or nintedanib arm in a 1:2 fashion using a stratified permuted block randomization scheme. The randomization lists to be used in this study will be generated by the study biostatistician. Patients will be included in data analyses according to their randomized treatment assignment irrespective of the treatment actually received (intent-to-treat). After randomization, initiation of the study intervention will take place once symptoms arise for the patient, this will be left to the patient's discretion. Patient randomization will be done by the Department of Biostatistics at Roswell Park.

INVESTIGATOR STUDY ELIGIBILITY VERIFICATION FORM

Participant Name: (Network sites use participant initials): _____

Medical Record No.: (Network sites use participant ID): _____

Title: A Phase II Randomized, Double-Blind, Placebo-Controlled Study Evaluating Nintedanib versus Placebo as Prophylaxis against Radiation Pneumonitis in Patients with Unresectable NSCLC Undergoing Chemoradiation Therapy

INCLUSION CRITERIA				
Yes	No	N/A	All answers must be "Yes" or "N/A" for participant enrollment.	Date
			1. Age 18 years or greater.	
			2. Histologically or cytologically-proven non squamous cell NSCLC. Mixed histology with SCLC component not allowed.	
			3. Patients with Stage II – IV non squamous cell NSCLC who received at least 54 Gy of total planned thoracic radiation dose will be eligible. Patients must have received at least one cycle of chemotherapy concurrently during the course of thoracic radiation. Regimens allowed are platinum combinations with either etoposide or a taxane regardless of histology subtype; platinum with pemetrexed for patients with nonsquamous NSCLC only. Patients with oligometastatic Stage IV cancer are eligible if they have received only one line of systemic therapy for their Stage IV cancer prior to the concurrent chemoradiation phase.	
			4. Patient must have had a CR/PR/SD, 4-6 weeks after completing last fraction of radiation therapy.	
			5. ECOG Performance Score 0-2.	
			6. ANC \geq 1,500/ μ L.	
			7. Platelet count \geq 100,000/ μ L.	
			8. Hemoglobin \geq 9 g/dL.	
			9. Total bilirubin \leq normal or for patients with Gilbert's syndrome, \leq 1.5 times upper limit of normal (ULN) OR direct bilirubin normal (per institute standards).	
			10. AST \leq 1.5 x ULN. ALT and AST \leq 2.5 x ULN is acceptable if there is liver metastasis.	
			11. Fertile patients must use adequate contraception.	

Investigator Signature: _____ **Date:** _____

Printed Name of Investigator: _____

INVESTIGATOR STUDY ELIGIBILITY VERIFICATION FORM

Participant Name: (Network sites use participant initials): _____

Medical Record No.: (Network sites use participant ID): _____

Title: A Phase II Randomized, Double-Blind, Placebo-Controlled Study Evaluating Nintedanib versus Placebo as Prophylaxis against Radiation Pneumonitis in Patients with Unresectable NSCLC Undergoing Chemoradiation Therapy

EXCLUSION CRITERIA				
Yes	No	N/A	All answers must be “No” or “N/A” for participant enrollment.	Date
			1. WBRT < 14 days from the anticipated start of nintedanib/placebo administration.	
			2. Squamous cell NSCLC	
			3. Unable to start nintedanib/placebo treatment between 4 - 8 weeks after completing the last dose of thoracic radiation.	
			4. Active untreated brain or leptomeningeal metastases. In patients with treated CNS metastases, eligible if symptoms controlled for at least 4 weeks. Dexamethasone allowed if total daily dose does not exceed 2 mg.	
			5. Major injuries or surgery (e.g., craniotomy) < 28 days from the start of nintedanib/placebo administration. Wound should be healed prior to starting therapy.	
			6. Second malignancies are allowed as long as the disease does not require active treatment with concomitant systemic cytotoxic chemotherapy, investigational or biologic therapy (e.g., anti-CTLA4 or HER2 monoclonal antibodies). Hormone-related therapies (e.g., LHRH agonists, tamoxifen, etc.) are allowed.	
			7. Concurrent uncontrolled illness including, but not limited to, ongoing or active infection, symptomatic congestive heart failure, unstable angina pectoris, cardiac arrhythmia, or psychiatric illness/social situation that would increase the risk associated with study participation and/or limit compliance with study requirements.	
			8. Inability to swallow study medication.	
			9. Presence of active malabsorption disorder (e.g., flare episodes documented within the preceding 3 months, presence of symptoms requiring daily medications for control) or history of extensive small bowel resection.	
			10. Known bleeding or thrombotic diathesis.	

EXCLUSION CRITERIA				
Yes	No	N/A	All answers must be "No" or "N/A" for participant enrollment.	Date
			11. History of arterial or venous thromboembolic event within 12 months prior to study participation.	
			12. Active hemoptysis or history of clinically relevant hemoptysis as determined by the treating physician. Patients who had history of transient minor hemoptysis after bronchoscopic biopsy are eligible unless deemed otherwise by the treating physician.	
			13. CTCAE Grade 2 or higher proteinuria.	
			14. Investigational agent administered < 28 days prior to treatment with nintedanib. Last dose of systemic chemotherapy administered < 14 days prior to treatment with nintedanib.	
			15. Known chronic active hepatitis B or hepatitis C. HIV-positive patients receiving or are candidates for antiretroviral therapy are also excluded.	
			16. Pregnancy or breast feeding. Female patients with child-bearing potential must have a negative pregnancy test (β -HCG test in urine or serum) prior to commencing study treatment.	
			17. Creatinine > 1.5 x ULN or CrCL < 45 mL/min. Refer to Appendix D .	
			18. Centrally located tumors with radiographic evidence (CT or MRI) of local invasion of major blood vessels.	
			19. Therapeutic anticoagulation (except low-dose heparin and/or heparin flush as needed for maintenance of an in-dwelling intravenous device) or anti-platelet therapy (except for low-dose therapy with acetylsalicylic acid < 325 mg per day).	
			20. Active or previous autoimmune disease requiring treatment within the past 2 years will exclude patients from receiving immune checkpoint inhibitor in this study. Exception allowed: Endocrine conditions treated with necessary hormone replacement or other supportive medication; vitiligo, alopecia.	

Participant meets all entry criteria: Yes No
If "NO", do not enroll participant in study.

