7 TREATMENT PLAN

7.1 Dosing and Administration

Treatment will be administered on an outpatient basis. Each cycle will be 28 days. Patients will be dispensed sufficient supply for at least 28 days or until their next scheduled visit. Reported adverse events (AEs) and potential risks are described in **Section 1.6**. Appropriate dose modifications are described in **Section Error! Reference source not found.**

With the November 2018 amendment allowing immune checkpoint inhibitor such as durvalumab consolidation therapy, a conventional dose-escalation design will be explored for patients who will be receiving durvalumab. Patients enrolled in the dose-escalation portion must commence nintedanib dosing at the same time as durvalumab is started. Dosing with nintedanib will start at 100 mg BID (see Table 1).

For patients who will be receiving durvalumab as standard of care prior to establishment of the recommended phase II dose of this combination, they will NOT undergo randomization (i.e. not blinded to treatment) and will receive active drug (nintedanib) on the first day of the first dose of durvalumab 10mg/kg every 2 weeks for up to 12 months.

All administered doses of the study drugs will be recorded in a pill diary to be provided to the patient (**Appendix E**).

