- QOL Questionnaire (Cycle 3 and Cycle 6 only) (Appendix F)
- ECOG Performance Status (Appendix C)
- Tumor/Disease Assessment (Cycle 3 and Cycle 6 only)
- Dispense nintedanib/Placebo
- Concomitant Medications
- Adverse Events

9.5 Evaluations Performed Anytime When Radiation Pneumonitis is Suspected to Have Occurred (Within the First 6 Months After Completing Radiation Therapy)

- Medical history
- Physical examination, including vital signs (i.e., temperature, heart rate, respiratory rate, blood pressure, and body weight)
- Hematology [(i.e., complete blood count (CBC) with automated differentials)](or, the physicians' discretion): WBC, RBC, HGB, HCT, platelet, MCV, MCH, MCHC, % neutrophils, absolute neutrophils, % monocytes, absolute monocytes, % eosinophils, absolute eosinophils, % basophils, absolute basophils, % lymphocyte total, absolute lymphocyte total, platelet confirmation (as clinically indicated), and differential confirmation (as clinically indicated). Note: Participants experiencing Grade 4 neutropenia should be monitored according to institutional guidelines. As needed at each study visit as determined by the Investigator or study physician.
- Chemistry (i.e., complete metabolic panel (CMP): chloride, CO₂, potassium, sodium, BUN, glucose, calcium, creatinine, total protein, albumin, total bilirubin, alkaline phosphatase, AST, ALT, A/G ratio, BUN/creatinine ratio, osmol (Calc), anion gap).
- Mitochondrial DNA Assay (one 10 mL heparinized green-top tube)
- QOL Questionnaire (Appendix F)
- ECOG Performance Status (Appendix C)
- Tumor/Disease Assessment
- Concomitant Medications
- Adverse Events

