- 1 Performed within 4 weeks prior to initiation of treatment.
- 2 Follow-up to 2.5 years after completing nintedanib/placebo treatment to be conducted as part of routine/standard care. Information may be conducted by phone only if patient relocated/unable to return to treating institution(if patient unable to return, phone call follow-up includes QOL Questionnaire ([Appendix F](#)) only if possible).
- 3 Height collected at baseline only.
- 4 Hematology [(i.e., complete blood count (CBC) with automated differentials)](or, the physicians’ discretion): WBC, RBC, HGB, HCT, platelet, MCV, MCH, MCHC, % neutrophils, absolute neutrophils, % monocytes, absolute monocytes, % eosinophils, absolute eosinophils, % basophils, absolute basophils, % lymphocyte total, absolute lymphocyte total, platelet confirmation (as clinically indicated), and differential confirmation (as clinically indicated). Note: Participants experiencing Grade 4 neutropenia should be monitored according to institutional guidelines. As needed at each study visit as determined by the Investigator or study physician.
- 5 Chemistry (i.e., complete metabolic panel (CMP): chloride, CO₂, potassium, sodium, BUN, glucose, calcium, creatinine, total protein, albumin, total bilirubin, alkaline phosphatase, AST, ALT, A/G ratio, BUN/creatinine ratio, osmol (Calc), anion gap).
- 6 For routine tumor assessment, CT abdomen and pelvis with high-resolution CT chest (HRCT) should be obtained. HRCT chest alone will be sufficient whenever new onset of dyspnea occurs and radiation pneumonitis is suspected to have occurred (within the first 6 months after completing radiation therapy). CT chest obtained/configured at 1.25 mm slice thickness is an acceptable alternative to HRCT. Maximum slice thickness allowed for CT chest is 2.5 mm. Use of intravenous contrast for the CT studies is preferred but not mandatory.
- 7 To be performed prior to drug administration on Day 1 of Cycles 3 and 6 (± 7 days window) only.
- 8 Medications ongoing within 1 week prior to first dose of study drug.
- 9 Sample collection will be obtained anytime when radiation pneumonitis is suspected to have occurred (within the first 6 months after completing radiation therapy).
- 10 Urinalysis after baseline will be performed per clinical discretion / judgement.
- 11 For females of child-bearing potential.

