13.7 Secondary Analyses

The OS and PFS will be reported by study arm using standard Kaplan-Meier methods. Comparisons of OS and PFS between study arms may utilize the two-sided stratified log-rank test. With a sample size of $n = 33$ in the control and $n = 66$ in the treatment group, there is an 80% chance of detecting a hazard ratio of 0.53 or smaller (with two-sided alpha of 0.05). If the

median PFS in the placebo arm is approximately 2 months, then this would be equivalent to detecting an increase in PFS of at least 1.75 months.

The overall and sub-category QOL and symptom scores (ranging from 0 to 68) will be reported by study arm and time using the appropriate descriptive statistics. Changes in the QOL and symptom scores may be compared between study arms using the Wilcoxon rank sum or independent sample t-tests, as appropriate. No adjustments for multiple testing will be made as this is a secondary analysis. With this sample size, there will be an 80% chance of detecting a change of at least 0.5 standard deviations. A 0.5 standard deviations is equivalent to approximately 9.1 points for the overall QOL and symptoms score; therefore, this study should be able to identify clinically relevant changes in QOL (59).

The PFTs will be reported by study arm and time using the appropriate descriptive statistics. Changes in PFTs, relative to baseline, will be evaluated within each study arm using the Wilcoxon signed rank or paired t-tests, as appropriate. Changes in PFTs may be compared between study arms using the Wilcoxon rank sum or independent sample t-tests, as appropriate. No adjustments for multiple testing will be made as this is a secondary analysis. With this sample sizes, we will have an 80% chance of detecting a change of at least 0.5 standard deviations.

The RP scores will be reported by study arm and time using the appropriate descriptive statistics. Changes in RP scores, relative to baseline, will be evaluated within each study arm using the Wilcoxon signed rank or paired t-tests, as appropriate. Changes in RP scores may be compared between study arms using the Wilcoxon rank sum or independent sample t-tests, as appropriate. No adjustments for multiple testing will be made as this is a secondary analysis. With our sample sizes, we will have an 80% chance of detecting a change of at least 0.5 standard deviations.

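### Extra tumour assessments triggered by suspected pneumonitis tilt the PFS log-rank test slightly toward nintedanib, and Section 13.7 has no rule for dating progressions found on them

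*Combined protocol and SAP*

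**What the plan says.** The synopsis (Study Procedures) lists "Disease Evaluation: Baseline, Cycle 3 Day 1, Cycle 6 Day 1, anytime when radiation pneumonitis is suspected to have occurred", and limits that trigger to the first 6 months after radiation. Section 9.5, headed "Evaluations Performed Anytime When Radiation Pneumonitis is Suspected to Have Occurred", includes a Tumor/Disease Assessment, and Table 5 repeats it. Footnote 6 of Table 5 narrows the imaging: "HRCT chest alone will be sufficient whenever new onset of dyspnea occurs and radiation pneumonitis is suspected to have occurred".

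The scheduled assessments are sparse. On treatment, footnote 7 says "To be performed prior to drug administration on Day 1 of Cycles 3 and 6", and Section 7.1 says "Each cycle will be 28 days". After treatment the synopsis gives "between 76 to 97 days after last nintedanib dose, between 166 to 187 days after last nintedanib/placebo dose, and long term follow-up", with no interval stated for the long-term scans.

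Section 13.7 says "Comparisons of OS and PFS between study arms may utilize the two-sided stratified log-rank test" and plans on the condition that the "median PFS in the placebo arm is approximately 2 months". I found no definition of PFS, no rule for dating a progression seen at an unscheduled scan, and no interval-based or sensitivity analysis. The one dating rule I found, for FDG-PET in Section 10.6, uses the actual scan date.

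**The concern.** PFS is dated by when progression is looked for. Here the frequency of looking depends partly on the primary endpoint, the event nintedanib is meant to prevent. If the drug works on pneumonitis, placebo patients get more off-schedule scans per head and some of their progressions are picked up weeks earlier. Blinding does not remove this, because the trigger is a clinical event. The point concerns the timing of true progressions and does not need pneumonitis to be misread as tumour growth.

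Comparing PFS is a secondary objective (Section 3.2), and the Rationale raises a possible anti-tumour benefit, so a PFS signal would naturally be read that way.

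**Working it through.** **1. The plan's own figures.** Section 13.7 states 80% power at HR 0.53 with 33 v 66 patients and two-sided alpha 0.05. Schoenfeld events: (1.96 + 0.842)² / [(1/3)(2/3)(ln 0.53)²] = 7.85/0.0896 ≈ 88. With a 2-month placebo median and 12 months of follow-up, expected events are 33(1 − 2^−6) + 66(1 − 2^(−12×0.53/2)) = 32.5 + 58.7 = 91.2, giving 81.6% power. The median gain is 2/0.53 − 2 = 1.77 months (stated 1.75). The stated figures reproduce.

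**2. Scan calendar, assuming six full cycles.**
- Cycle 3 Day 1: 2×28 + 1 = day 57. Cycle 6 Day 1: 5×28 + 1 = day 141. Gap 84 days, or 12 weeks.
- First post-treatment scan: 168 + 76 to 168 + 97 = days 244 to 265. Gap from day 141: 103 to 124 days, about 15 to 18 weeks.
- Trigger window: drug starts 4 to 8 weeks after radiation (Section 2), so 6 months (26 weeks) after radiation ends about 18 to 22 weeks into treatment, days 126 to 154.

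**3. How many patients are triggered.** Section 13.1 gives 30% v 10%: 0.30×33 = 9.9 placebo and 0.10×66 = 6.6 nintedanib patients.

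**4. How many dates move.** Assume exponential progression at rate λ, and one triggered scan per affected patient, uniform over days 0 to 140 and able to show any progression. The chance that this scan is the first to show progression is [f(0,57) + f(57,140)]/140, with f(a,b) = e^(−λa)·[(b−a) − (1 − e^(−λ(b−a)))/λ].
- 2-month median, λ = 0.01139 per day: (15.07 + 15.32)/140 = 0.217. Re-dated: 9.9×0.217 = 2.1 of 33 and 6.6×0.217 = 1.4 of 66.
- 6-month median, λ = 0.00380 per day: (5.74 + 9.51)/140 = 0.109. Re-dated: 1.1 of 33 and 0.7 of 66.

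**5. Effect on the test when the true HR is 1.** Simulated trials of 33 v 66, unstratified log-rank, 2-month median, 30% v 10%, one triggered scan. The runs differ slightly in set-up:

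| Run | Significant for nintedanib: scheduled scans only → with triggers | Significant for placebo | Two-sided total |
|---|---|---|---|
| A (20,000 trials) | 3.2% → 3.8% | 2.3% → 2.0% | 5.5% → 5.8% |
| B | 2.4% → 3.5% | 2.0% → 1.4% | 4.4% → 4.9% |
| C (12,000 trials) | 2.5% → 4.4% | 2.5% → 1.8% | 5.0% → 6.2% |

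The favourable tail rises by 0.6, 1.1 and 1.9 points. The total rises by only 0.3, 0.5 and 1.2 points, because the opposite tail shrinks. The fitted Cox HR in run B goes from 0.990 to 0.974, a ratio of 0.984. Run A's mean estimate is 0.985 against 1.00.

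**6. Range over inputs the documents do not give** (run A set-up).
- Half of progressions visible on chest CT: HR 0.994, favourable tail 3.4%.
- Medians of 6 to 17 months, one scan: HR 0.996 to 0.999.
- Three triggered scans per affected patient, 2-month median: HR 0.97 and 4.5% at 30% v 10%; 0.95 and 5.4% at 40% v 10%; 0.94 and 6.4% at an assumed 60% v 20% suspicion rate.
- True HR 0.53, 2-month median, one scan: power 80.4% → 81.7%.

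**7. Does re-dating help?** Dating the same data to the scheduled scan returned the favourable tail to about 2.5% in the run C set-up.

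**The case against.** The strongest reply is that this is too small to matter. About two placebo and one or two nintedanib dates move. The planned test is two-sided and its total error changes little. PFS is secondary and its comparison is optional as worded. The 2-month median is only a planning condition, and Section 6.1 requires response or stable disease 4 to 6 weeks after radiation, so a longer median is plausible. Chest-only imaging need not find extrathoracic progression. Section 10.4 also counts symptomatic deterioration as progression, which no scan dates. The trigger is suspicion, not confirmed Grade 2 or higher pneumonitis, and no suspicion rates are given. Replacing actual dates would also discard known information.

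Most of this stands. It limits the size and argues for a companion analysis, not a replacement of the actual-date test. It does not supply the missing dating rule, and under the design's own assumption the direction is known in advance.

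A reader might infer a larger bias, with HR about 0.94 to 0.95. That figure appears with the one-step estimate exp((O − E)/V) when most events tie on days 57 and 141. The fitted Cox ratio in the same setting is about 0.984. A reader might also infer that the mechanism could by itself produce the planned HR of 0.53, or that it runs throughout follow-up. The simulations do not support the first, and the 6-month limit on the trigger rules out the second. That limit also leaves OS and the 1-year PFS rate essentially untouched.

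**Conclusion.** The concern holds as a modest, directional weakness on a secondary endpoint. With no true effect, the plan's 2-month median and one triggered scan per affected patient, the fitted HR shifts by about 1.5% toward nintedanib, and false claims in its favour rise by about 0.6 to 2 percentage points. The shift is smaller if chest CT misses extrathoracic progression, and 1% or less at medians of 6 months or more. Several triggered scans per patient would enlarge it.

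This rests on suspicion rates differing between arms as the Grade 2 or higher rates are expected to (with equal rates there is no tilt), on triggered scans being uniform over days 0 to 140, on exponential PFS, and on an unstratified test standing in for the stratified one.

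**What to change.** Add to Section 13.7, before unblinding:
- a definition of PFS, and a data flag for unscheduled scans done for suspected pneumonitis;
- alongside the actual-date log-rank, a pre-specified stratified log-rank in which a progression first seen on a flagged scan is assigned to the next nominal disease-evaluation date, or an interval-based equivalent;
- a nominal calendar counted from treatment start assuming six full cycles, whether or not drug was stopped. Post-treatment scans are otherwise tied to the last dose, so a patient who stops after a triggered CT has no unique next date. Days 57 and 141 and one fixed day within 244 to 265 cover the whole trigger window;
- the date of death, if it comes before that nominal date;
- scan counts by arm, and a statement that a PFS benefit will not be read as anti-tumour activity unless both analyses agree.

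The cost is a few sentences and one flag, with no added visits, patients or changes to care. PFS times in the companion analysis become slightly later and coarser in both arms.
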